7.2.3 Secondary endpoint analyses

[figure not shown]
For the list of key secondary and secondary endpoints, refer to [Section 2.1.3](#). Summary statistics will be presented for each endpoint, and at each visit if appropriate.

The key secondary endpoints are both binary in nature and will be analysed using frequency tables, risk differences, 95% confidence intervals and p-values. The delta method and average marginal effect (AME) method will be used. In the NIV cohort, adjustment will be made for the number of days under NIV support, baseline D-Dimer level and age. For the IMV cohort, adjustment will be made for the baseline WHO value, baseline D-Dimer level and age.

For the safety endpoint (MBE to Day 6) which is binary, the Chang and Zhang exact method will be used, without adjustment for covariates.

The continuous endpoints will be analysed descriptively and inferentially, albeit in a non- confirmatory manner. A restricted maximum likelihood (REML) based ANCOVA will be used. In the NIV cohort, adjustment will be made for the number of days under NIV support, baseline D-Dimer level and age. For the IMV cohort, adjustment will be made for the baseline WHO value, baseline D-Dimer level and age. The treatment difference with 95% confidence interval will be presented.

More detailed descriptions will be provided in the TSAP.

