7.5 DETERMINATION OF SAMPLE SIZE

Part 1 of the study plans to randomise approximately 60 patients in total, with a view to exploring the data in a descriptive manner.

Sample size considerations are limited to Part 2 and the NIV patient cohort.

Part 2 has a planned confirmatory analysis at the 2-sided type I error level of alpha=5% with a power of 85% to 90%, applicable to the first two steps within the pre-planned hierachial testing procedure. The trial uses a randomisation allocation ratio of 2:1, which leads to approximately 140 NIV patients on the treatment arm and approximately 70 NIV patients on the SOC alone.

With regard to the primary analysis of the primary endpoint, H0_1 in the hierarchy testing procedure, in the NIV patient cohort, a hazard ratio of 2.0 is assumed, with event rates in the SOC alone group and alteplase group of approximately 30% and 50%. In the alteplase arm, it is expected to have a median time to event of 20 to 30 days.

With regard to the primary analysis of the key secondary endpoint “Treatment failure at Day 28”, H0_2 in the hierarchy testing procedure, in the NIV patient cohort, a risk difference of -20% is assumed, with event rates in the SOC alone group and alteplase group of approximately 40% and 20%.

With regard to the primary analysis of the key secondary endpoint “All cause mortality at Day 28”, H0_3 in the hierarchy testing procedure, in the NIV patient cohort, there would be a power of 85% under the assumptions of a risk difference of -16%. This would be with event rates in the SOC alone group and alteplase group of approximately 25% and 9%. These are very similar event rates as observed in Part 1.

The sample size determination or justification is in line with the null hypotheses and hierachial testing approach as defined in [Section 7.1](#), whereby it is planned to test for superiority of alteplase vs SOC alone in the NIV patient cohort. Whilst the assumptions are still rather approximate, the magnitude of these assumptions is similar to the available results

in other COVID-19 patients [[R20-2001](#), [R20-2246](#)] and to the results observed in Part 1 of this study. In this emerging disease and during this pandemic, standard of care is evolving, and other factors are having an influence, for example, the introduction of vaccines.

Calculations were performed using the software R Version 3.6.1 and nQuery Version 4.0.

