- If day 6 value is missing, no Day 5 value available, but day 7 available, then day 7 value will be used
- Otherwise value set to missing for that patient.

Based upon this, the change from baseline for each patient will be calculated and used for the analysis.

Number of oxygen-free days (OFD) up to day 28, FAS, continuous endpoint

For this endpoint, 'oxygen-free' is defined as free from assistance from oxygen support. The number of oxygen-free days starts from when the patient has a 'lasting' value on the WHO clinical progression scale of ≤ 4 and ends on Day 28. A lasting value of ≤ 4 means that the value cannot exceed 4 at a later timepoint. If the patient is liberated from oxygen on Day x, then the number of OFDs is 28-x. If a patient has withdrawn consent prior to day 28 then he will have a missing value for OFD. In any case, if the status of the patient at Day 28 is death, as determined from the vital status page then the OFD=0.

Length of hospital stay up to day 28, FAS, continuous endpoint

This will be determined based upon the first hospital discharge date, or discharge to another care facility. If the patient dies within the first 28 day period, then length of hospital stay is 28.

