7.5.2 Other Secondary endpoints

Other secondary endpoints are defined in [Section 5.2.2](#). In all cases, standard descriptive statistics will be presented, whether the endpoint is binary or continuous.

Binary safety endpoint

For the binary safety endpoint MBE up to day 6, analysed on the TS, there will be no adjustment for covariates. Therefore, the RD will be the difference between the two incidences and the p-value and 95% CI will be determined using the Chan and Zhang exact method.

For the NIV and IMV cohorts pooled, the RD 95% CI will be estimated between the two treatment arms using the same approach as for the key secondary efficacy endpoints. However, for this pooled investigation of MBE up to day 6, the baseline D-Dimer status (≥ 3 to <5 , ≥ 5 -fold ULN) and age covariates will not be included in the model. The p-value for homogeneity will be determined similarly.

Continuous efficacy endpoints

The three other secondary endpoints which are continuous in nature will be analysed using a restricted maximum likelihood (REML) based ANCOVA comparing the outcome, by treatment. The ANCOVA model will be adjusted for the default set of covariates as outlined in [Section 7](#) for the respective NIV and IMV patient cohorts. The treatment difference with 95% CI and p-values will be presented.

For the continuous efficacy endpoints, number of OFDs at day 28, and number of days in hospital, there are not expected to be any missing values by definition and as outlined in [Section 5.2.2](#).

[figure not shown]
For the continuous efficacy endpoint change from baseline in the $\text{PaO}_2/\text{FiO}_2$ at day 6, the baseline $\text{PaO}_2/\text{FiO}_2$ will also be included in the model as covariate for adjustment. For patients that have died, or who have been discharged from hospital, the handling rules are as outlined in [Section 5.2.2](#). Note, there are expected to be very few deaths or hospital discharges prior to day 6.

In addition, subgroup analyses of this $\text{PaO}_2/\text{FiO}_2$ endpoint will be conducted in the NIV patient cohort only and using the subgroups as outlined in [Section 6.4](#). An ANCOVA model will contain the baseline $\text{PaO}_2/\text{FiO}_2$, the subgroup of interest and the interaction between subgroup and treatment.

As sensitivity analyses, the unadjusted treatment effects will be estimated, using the same approach as the main analysis, but with only treatment in the model.

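### The ANCOVA of oxygen-free days and hospital stay states no variance structure; near the planned recovery rates, one residual variance with 2:1 allocation makes the 95% interval roughly 3% to 7% too wide

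*SAP*

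**What the plan says.** Protocol 7.2.3 says of the continuous secondary endpoints: "A restricted maximum likelihood (REML) based ANCOVA will be used". SAP (Part 2) 7.5.2 repeats this as a "restricted maximum likelihood (REML) based ANCOVA comparing the outcome, by treatment", and reports the difference with a 95% interval and p-value. On covariates: "The ANCOVA model will be adjusted for the default set of covariates as outlined in" Section 7. For the NIV cohort these are D-dimer stratum, age and days of NIV support. Neither document mentions a variance by arm, a robust standard error or a degrees-of-freedom method.

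SAP 5.2.2 counts oxygen-free days (OFD) as 28 minus the day on which the patient lastingly reaches WHO 4 or below. For deaths: "In any case, if the status of the patient at Day 28 is death, as determined from the vital status page then the OFD=0". A patient who dies within 28 days is given a hospital stay of 28.

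Protocol 7.5 plans "approximately 140 NIV patients on the treatment arm and approximately 70 NIV patients on the SOC alone", and for the primary endpoint "a hazard ratio of 2.0 is assumed, with event rates in the SOC alone group and alteplase group of approximately 30% and 50" per cent. Of the alteplase arm it says "it is expected to have a median time to event of 20 to 30 days". No standard deviation, recovery rate or power is given for oxygen-free days or hospital stay.

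**The concern.** An ANCOVA with one residual variance gives the right standard error under unequal variances only if the arms are of equal size. At 2:1 it gives too much weight to the variance of the larger arm. If that arm is the more variable, the interval is too wide; if it is the less variable, too narrow.

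Unequal variances are to be expected for these two outcomes. The NIV cohort starts at WHO 6, so a two-point improvement is WHO 4, the state that starts the OFD count. Patients who never get there sit at 0, as do deaths. Hospital stay mirrors this at 28. The spread therefore follows the share who leave the boundary, and a treatment that changes that share changes the variance too. At stake are the error bars and p-values of two reported secondary endpoints, not a confirmatory test.

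**Working it through.** **Inputs from the documents.** 140 alteplase, 70 standard of care (SOC); event by Day 28 in 50% vs 30% (protocol 7.5); the OFD definition (SAP 5.2.2). **Assumed.** The primary-endpoint rates apply to lasting freedom from oxygen; the shape of the event-time distribution is varied, because the documents give none; one residual variance is the default reading.

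**The plan's own figure.** Protocol 7.5 states a "2-sided type I error level of alpha=5% with a power of 85% to 90" per cent for the first two steps. Expected events are 0.30 × 70 + 0.50 × 140 = 91. With hazard ratio 2.0 and 2:1 allocation, z = √(91 × 2/9) × ln 2 − 1.96 = 3.117 − 1.96 = 1.157, so power is 87.6%. Treatment failure (40% vs 20%) gives 86.0% and mortality (25% vs 9%) 85.1%. The plan's numbers reproduce, and they are the rates used here.

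**Formula.** Let v1 be the alteplase variance, v0 the SOC variance and r = v1/v0. At 140 vs 70:
- true SE² = v1/140 + v0/70 = (v1 + 2v0)/140
- one-variance SE² ≈ (2v1 + v0)/140
- ratio of SEs = √[(2r + 1)/(r + 2)]

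**Uniform event times over 28 days.** With OFD = max(28 − T, 0) and recovery probability p, the variance is (784/3)p − 196p².
- SOC, p = 0.30: 78.40 − 17.64 = 60.76, SD 7.8
- Alteplase, p = 0.50: 130.67 − 49.00 = 81.67, SD 9.0
- r = 1.344; ratio = √(3.688/3.344) = 1.050

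The standard error is 5.0% too large. After allowing for degrees of freedom, the interval is 4.9% wider than with separate variances. True coverage is 96.2%.

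**Other shapes at 30% vs 50%.**
- Exponential: SD 8.1 vs 9.6, r = 1.41. The one-variance SE is 1.34 against a true 1.27 (5.9% too large); the interval is 5.7% wider and coverage is 96.3%.
- Weibull shapes 0.01 to 3: interval 2.8% to 7.0% wider.

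**Covariate-adjusted simulation** (three covariates, 2,000 runs per scenario, REML with one variance or one per arm). With prognostic covariates the one-variance interval is 3.0% to 5.4% wider. Separate variances give coverage of 94% to 95% and raise power by 1 to 3 points, for example from 73.9% to 75.5%. Covariate strength is assumed.

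**Other recovery rates (SOC vs alteplase).** The uniform-time ratio is from the same formula.

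| Rates | v0 | v1 | SE ratio |
|---|---|---|---|
| 50% vs 70% | 81.67 | 86.89 | 1.010 |
| 60% vs 80% | 86.24 | 83.63 | 0.995 |
| 30% vs 20% | 60.76 | 44.43 | 0.950 |

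At 50% vs 70% the adjusted simulation shows a gap of 0.4%. At 30% vs 20% it shows a one-variance interval about 5% too narrow, with coverage of 93.8%. With no effect (30% vs 30%), type I error is 5.1% with one variance and 5.3% with two.

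**Cost if the variances are equal.** At 140 vs 70, degrees of freedom fall from 208 to about 138 and the interval widens by 0.3%. At 32 vs 16, the most expected in the invasive ventilation (IMV) cohort, it widens by 1.4%.

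**The case against.** The strongest reply is that nothing here is fixed by the documents. The SAP neither states one variance nor rules out two. The 30% vs 50% belongs to another endpoint, and protocol 7.5 itself calls its assumptions approximate. Exponential times with hazard ratio 2 across the stated alteplase median of 20 to 30 days give standard errors 4.1% to 6.6% too large. The Part 1 figures in protocol 1.1 (median 19 days, difference 19.1%, mixed ventilation types) give about 2.5%. The analyses are non-confirmatory, the error at the planned effect is conservative, and type I error is near 5% either way. All of this stands. It limits the size and importance of the point but does not remove it, because the default reading of an ANCOVA with no stated structure is one variance.

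A reader might infer more, and four such readings are not supported:
- *The intervals are wrong by a known amount.* No document gives a spread, a recovery rate for these endpoints or an event-time shape, so only a range can be given.
- *The problem disappears only if the drug does nothing.* The variance peaks and then falls as recovery rises. A real 20-point benefit can leave almost no gap (50% vs 70%) or reverse its sign (60% vs 80%).
- *PaO2/FiO2 change and the IMV cohort are affected in the same way.* PaO2/FiO2 change has no such boundary, and the size of any gap in the IMV cohort has not been established.
- *Separate variances cost nothing.* The cost is small, but not zero.

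**Conclusion.** The point holds as a minor improvement. With recovery near 30% vs 50% in the NIV cohort and one residual variance, the 95% interval for oxygen-free days is roughly 3% to 7% too wide, or about 3% to 5% after covariate adjustment. Coverage is then about 96%, and 1 to 3 points of power are lost. The same applies to hospital stay only if discharge rates resemble the planned rates, which the documents do not say. At 30% vs 20%, with alteplase worse, the interval would be about 5% too narrow, so the default is not safe in every direction. Both endpoints lie outside the confirmatory hierarchy, and no primary or key secondary conclusion changes.

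**What to change.** Add to SAP (Part 2) 7.5.2: for oxygen-free days and length of hospital stay in the NIV cohort, the residual variance is estimated separately by arm within the same REML model, with Satterthwaite or Kenward-Roger degrees of freedom. Heteroscedasticity-consistent standard errors would also serve.

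The cost is one sentence, one program option and an interval about 0.3% wider if the variances turn out equal. The Part 2 SAP is written to protocol Version 3 and still uses D-dimer strata starting at 3-fold ULN, while the current protocol starts them at ULN. It therefore needs revision anyway, and this line can go in then. Leave PaO2/FiO2 change and the IMV cohort as they are on this argument.

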7.7 EXTENT OF EXPOSURE

Exposure will be handled descriptively.

The number of patients with initial 2h infusion on day 1, optional 2h between days 2 and 5, and longterm 12h infusion over the five days of treatment will be summarized, as well as the rate of infusion (mL/kg/h) and duration of infusion (h).

The cumulative exposure will be presented, in terms of Total number of days of infusion. Exposure is relevant for the alteplase treatment groups only.

Within this section, all analyses will be performed on the NIV patient cohort, the IMV patient cohort and on the NIV and IMV cohorts pooled.

7.8 SAFETY ANALYSIS

The safety analysis will be performed as outlined in the CTP Version 3, according to BI standards and on the TS. For further details please see guideline 'Handling and summarization of AE data for clinical trial reports and integrated summaries' ([10](#)).

The definition of 'on treatment' is outlined in [Section 6.7](#). Any potential events starting between the time of randomisation and the start of alteplase treatment, will be indicated as such in the listings.

In addition, to fulfil the requirements of the European Union (EU) Regulation 536/2014 (Annex V, Point 6) ([11](#)), the following information should be made available, for the lay summary or CTR:

- frequency of serious drug-related AEs by treatment, primary system organ class and preferred term.

Within this section, all analyses will be performed on the NIV patient cohort, the IMV patient cohort and on the NIV and IMV cohorts pooled.

7.8.1 Adverse Events

Unless otherwise specified, the analyses of AE will be descriptive in nature. All analyses of AEs will be based on the number of subjects with AEs and NOT on the number of AEs.

AEs will be coded using the most recent version of the Medical Dictionary for Regulatory Activities (MedDRA) coding dictionary

The analysis of AEs will be based on the concept of treatment emergent adverse events (TEAE). That means that all adverse events occurring 'on treatment' as outlined in [Section 6.7](#) will be considered as TEAE.

All AEs occurring before 'on treatment' will be assigned to 'screening' and all AEs occurring after 'on treatment' will be assigned to 'post-treatment'. In general, AEs attributed to 'Screening' or 'Post-treatment' will be listed only.

An overall summary of AEs will be presented.

Frequencies [N (%)] of patients with AEs will be summarised by treatment, primary system organ class and preferred term (using MedDRA). Separate tables will be provided for patients with serious adverse events.

The system organ classes will be sorted according to the standard sort order specified by European medicines agency (EMA), preferred terms will be sorted by frequency (within system organ class).

Additionally, the following analyses will be reported for disclosure on European Union Drug Regulating Authorities Clinical Trials Database (EudraCT) and clinicaltrials.gov:

- Frequency [N(%)] of patients with non-serious AEs occurring with incidence in preferred term greater than 5% by treatment,
- AEs per arm for disclosure on EudraCT by treatment
- Non-serious AEs for disclosure on EudraCT by treatment
- Serious AEs for disclosure on EudraCT by treatment

Adverse events of interest

All endpoints related to safety, outlined in [Section 5.2.2](#) and [Section 5.3](#), are clearly marked as such, in particular, endpoints related to MBE, Stroke, MI, PE and DVT. There is no further description below on how they should be analysed, however, they will be summarized with the safety data under the topic of 'AEs of special interest'.

There are two other AEs of special interest, which are not mentioned in [Sections 5.2.2](#) and [5.3](#):

- Transient ischemic attack
- Systemic embolism

AEs recorded on the AE page of the CRF, indicated as such via the relevant tick box, will be grouped and summarized using frequency tables.

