7.2.5 Safety analyses

Adverse events will be coded using the Medical Dictionary for Drug Regulatory Activities (MedDRA). Standard BI summary tables and listings will be produced. All adverse events with an onset between start of treatment and end of the REP, as defined in [Section 1.2.](#), will be assigned to the on-treatment period for evaluation.

All treated patients will be included in the safety analysis. In general, safety analyses will be descriptive in nature and will be based on BI standards. No hypothesis testing is planned.

Statistical analysis and reporting of adverse events will concentrate on treatment-emergent adverse events, i.e. all adverse events occurring between start of treatment and end of the REP. Adverse events that start before first drug administration and deteriorate under treatment will also be considered as 'treatment-emergent'.

Frequency, severity, and causal relationship of adverse events will be tabulated by system organ class and preferred term after coding according to the current version of MedDRA at DBL.

Laboratory data will be analysed quantitatively and qualitatively. The latter will be done via comparison of laboratory data to their reference ranges. Values outside the reference range as well as values defined as clinically relevant will be summarised. Treatment arms will be compared descriptively with regard to distribution parameters as well as with regard to frequency and percentage of patients with abnormal values or clinically relevant abnormal values.

Vital signs, physical examinations, or other safety-relevant data observed at screening, baseline, during the course of the trial and at the end-of-trial evaluation will be assessed with regard to possible changes compared with findings before start of treatment.

Further details on the safety analysis will be specified in the TSAP.

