6.7 BASELINE, TIME WINDOWS AND CALCULATED VISITS

Randomisation is defined as Day 1 and it is planned that the alteplase patients are administered their initial 2h infusion of study medication within 6 hours of randomisation, on Day 1 (Visit 2a). The last planned administration of study medication for the alteplase patients is the long term 12h infusion on Day 5.

Since all patients are on SOC and there is no clear start or stop of SOC, a fixed treatment duration will be used for all patients, for the purposes of the analyses. Therefore, endpoints referred to as ‘on treatment’ will include all relevant events from the relevant start point plus 288 hours (last planned treatment on Day 5 + 7 days of REP = 12 days = 288 hrs).

However, to take account of the fact that some patients may have had treatment interruptions, the residual effect period should be in relation to the last intake of alteplase infusion. [Table 6.7: 1](#) below outlines the time period definitions for counting on treatment safety event.

Table 6.7: 1 Time period for counting on treatment safety events

On treatment	Start point	End date
SOC patients	Randomisation date/time	Start point + 288 hrs
Alteplase patients	First administration of alteplase date/time	Latest of: 
 Start point + 288 hrs Last administration of alteplase date/time + 168 hrs

[Note: 288 hrs represents 12 days, 168 hrs represents 7 days]

According to CTP Version 3 Section 1.2, the residual effect period (REP) is 7 days.

As outlined in CTP Version 3 Section 7.2.1, the term "baseline" refers to the last observed measurement prior to randomisation on Day 1.

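### The Part 2 SAP drops the protocol's rule that an adverse event starting before the first dose and worsening on treatment is treatment-emergent, and does not declare the change

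*SAP*

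**What the plan says.** Protocol 7.2.5 defines treatment-emergent events in two parts. The first is "all adverse events occurring between start of treatment and end of the REP", the residual effect period. The second extends this: "Adverse events that start before first drug administration and deteriorate under treatment will also be considered as" treatment-emergent.

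Part 2 SAP 7.8.1 has only one part. It bases the analysis on treatment-emergent events and explains: "That means that all adverse events occurring 'on treatment' as outlined in" Section 6.7 count. It then disposes of the rest: "All AEs occurring before 'on treatment' will be assigned to 'screening' and all AEs occurring after" that period go to 'post-treatment'. It adds: "In general, AEs attributed to 'Screening' or 'Post-treatment' will be listed only". No exception for worsening is given.

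SAP Table 6.7:1 sets the start of 'on treatment'. For alteplase patients it is "First administration of alteplase date/time"; for SOC patients it is randomisation. SAP 7.8 says of the interval between the two: "Any potential events starting between the time of randomisation and the start of alteplase treatment, will be indicated as such in the listings". The same section says that the safety analysis follows Protocol Version 3 and company standards. SAP section 4, which lists changes from the protocol, mentions only two added analysis sets and added subgroup analyses.

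**The concern.** The two documents classify the same event differently. An event that begins before the first infusion and deteriorates during it belongs in the treatment-emergent tables under the protocol, and in a listing under the specific SAP rule. A programmer working from 7.8.1 would implement the SAP rule.

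Bleeding is the main known risk of alteplase, and the hours before the first dose are not clinically empty. Protocol 4.2.1 recommends that lines, tubes and drains be placed at least 6 h before the first treatment, and Protocol 1.4.3 notes that some Part 1 bleeds were related to interventions. A puncture-site bleed that starts before the thrombolytic and worsens under it is the kind of case the protocol clause covers. At stake is whether the safety tables follow the protocol's own definition.

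**Working it through.** The plan gives no figure to reproduce: these analyses are descriptive and the point is one of definition. The check is to classify the same event under each rule.

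| Onset and course | Protocol 7.2.5 | SAP 7.8.1, alteplase | SAP 7.8.1, SOC |
|---|---|---|---|
| Starts before randomisation, worsens during the on-treatment period | Treatment-emergent on alteplase; SOC has no first administration, so no literal anchor | 'Screening', listed | 'Screening', listed |
| Starts between randomisation and first dose, worsens later | Treatment-emergent on alteplase | 'Screening', flagged in listings | Treatment-emergent |
| Starts in the same gap, does not worsen | Not treatment-emergent on alteplase | 'Screening', flagged in listings | Treatment-emergent |
| Starts after first dose, within the window | Treatment-emergent on alteplase | Treatment-emergent | Treatment-emergent |

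On alteplase, rows 1 and 2 differ between protocol and SAP. That is the contradiction. Row 1 is lost in both arms. Rows 2 and 3 are where the arms differ, and they are confined to the gap, which Protocol 3.3 limits to 6 h. Row 3 follows from the different start points in Table 6.7:1, not from the missing clause.

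Such events are collected: Protocol 5.2.6.2.1 records all adverse events from consent onwards.

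A rough scale for bleed onsets, under stated assumptions:

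- Input: 3 SOC patients in Part 1 with non-major bleeding until Day 12 (Protocol 1.1). The denominator is 22, since the same section gives 9 SOC patients as 40.9%, and 9 / 0.409 = 22.
- Assumption: a constant rate over 12 days, carried over to pre-dose alteplase patients in the NIV cohort of about 140. The rate comes from a mixed Part 1 population and three patients. Line placement may cluster before dosing, which would raise it.
- Daily rate: 3 / 22 / 12 = 1.14% per day.
- Gap at its 6 h maximum: 1.14% × 140 × 6/24 = 0.4 alteplase patients with a bleed onset.
- Screening at the Flow Chart's 24 h: 1.14% × 140 = 1.6 alteplase patients, and 1.14% × 70 = 0.8 SOC patients.

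These are onsets, not losses. The loss is the onset count times the share that worsens on treatment, and the documents give no figure for that share. Nor do they give a rate for pre-dose events other than bleeds.

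One assumption concerns versions. The Part 2 SAP cites Protocol Version 3, while the protocol supplied is later. The log for Global Amendment 3 lists no change to section 7.2.5, so the worsening clause is taken to have been in Version 3.

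**The case against.** The strongest reply is that 7.8.1 is an abbreviated summary. Its parent section defers to the protocol and to a company guideline on adverse event handling that is not supplied, and the listing rule is qualified as general. This shows that an omission is more likely than a deliberate new rule. It does not remove the conflict: a specific sentence covering all earlier events sits beneath a general statement that implies otherwise, and the unseen guideline cannot be assumed to resolve it.

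A second reply is that Protocol 5.2.6.1.1 asks sites to record worsening of the underlying disease or of pre-existing conditions as an adverse event. If a site enters the worsening as a new event, its onset is on treatment and both rules agree. This could shrink the loss. The documents do not say that it applies to an event first recorded after consent.

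Three stronger readings are tempting and are not supported.

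- A reader might infer that the rule biases the comparison in favour of alteplase throughout. It does not: events starting before randomisation drop out in both arms, and the arm difference is limited to the gap. The alteplase window can also run longer than SOC's. On the nominal schedule the Day 5 infusion ends at hour 110; with the full 72 h of interruption and 168 h of residual effect, that is 110 + 72 + 168 = 350 h, against 288 h.
- A reader might infer that the major bleeding endpoint loses bleeds that start before the dose and become major under alteplase. SAP 5.2.2 counts the major bleed itself within its window and does not date it by the onset of an earlier minor bleed. A bleed that first meets the ISTH criteria after dosing fits that wording.
- A reader might put the loss at a definite number of patients. That needs a worsening share, and none is given. The tables also count patients, not events, so a patient with another on-treatment bleed still appears among patients with any bleed.

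**Conclusion.** The point holds as a contradiction of definition. SAP 7.8.1 narrows the protocol's definition of treatment-emergent events, section 4 does not say so, and SAP 7.8 says the opposite. Followed literally, pre-dose events that worsen on alteplase would be missing from the treatment-emergent tables.

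The practical size is small and cannot be derived. On the assumptions above, fewer than one alteplase patient in the NIV cohort would have a bleed starting in the only interval where the arms are treated differently, and only a share of those would worsen. The size is smaller still if sites enter worsening as a new event. Events starting in the gap remain visible in the listings. The confirmatory efficacy tests are unaffected. It should be corrected because the safety question concerns a thrombolytic and the correction is cheap.

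**What to change.** Add the protocol's clause to SAP 7.8.1: an adverse event that starts before the anchor and worsens during the on-treatment period is treatment-emergent. State the anchor for each arm: first alteplase administration for alteplase, randomisation for SOC. The SOC anchor needs stating because the protocol's wording refers to a drug administration that SOC patients do not have. If the narrower rule is intended, declare and justify it in SAP section 4.

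Optionally, state in SAP 5.2.2 that a major bleed is dated by when the ISTH criteria are first met. This is a clarification only.

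The cost is one or two sentences and no new visits. Alteplase event counts may become slightly less favourable. Worsening must be identifiable in the adverse event data, which the protocol rule already requires. Protocol 8.3.1 names only onset and end dates among its examples, so the eCRF should be checked. The clause does not remove the different start points: an event in the gap that does not worsen will still count in SOC only, and a footnote to the tables should say so.
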